
7.0
	
Overall
 
 Documentation of decision to discontinue the BRAIVE program. The CIP has been updated accordingly to reflect the changes. Enrollment stopped when 10 subjects were enrolled. Decision to not renew EC certification for the Braive GMS into the European Market. Relevant changes from most recent Clinical Investigation Plan Medtronic template version E have been implemented in the applicable sections. Removed external vendors: Explant and NAMSA 
Study endpoints:
 
 Updated study purpose and endpoints due to discontinuation of the BRAIVE program. Main focus on device/procedure safety: Updated primary endpoint "The primary safety endpoint is any secondary 	
██████████ Clinical Study Manager

spinal surgery defined as treatment failure up to 24 months postoperatively” to “device-related adverse events up to 24 month follow up”.

- Main Thoracic Cobb angle is a secondary endpoint
- Instrumented Cobb Angle added as an endpoint (already collected in previous CIP version)
- Removal of the following endpoints: Individual Subject Success, PedsQL, shoulder imbalance endpoint, T1-L1 length, disc wedging angle and Neurological status.

Schedule of Events

- Visits windows were widened to allow the investigators to plan the patient visits according to their growth.
- Updated Neurological Status (collected at preop and discharge)
- Updated pulmonary function (collected at preop)
- Updated PedsQL (collected at preop)
- Risser score: mandatory from 24 months onwards

Radiographic evaluation:

- Radiographic images will be evaluated by investigators. This is including radiographic endpoints assessment and Risser score evaluation (to assess skeletal maturity).
- Radiographic measures will be performed according to site standard of care (except for Risser score).
- Radiographic Core Lab had been used for eligibility assessment for all patients enrolled in the study.

Study committee/External organization

- Removal of CEC review because this committee was assessing secondary spinal surgeries for the primary safety endpoint analysis, which was modified.
- Explant analysis: the decision has been made that explanted device will be analyzed following Medtronic processes. The Histology lab and Analysis lab for explanted devices have been removed.
- Removal of DMC, instead, a steering committee and Medtronic medical advisor will monitor the safety of investigational treatment.

2.0	
 Updated to point to V3.0 of the protocol (CIP). (Due to lack of oversight the statistical programmer signature was missing. There is no impact for the study since no patients were enrolled yet and no data analysis took place under this version.) 	
██████████ M Squared Associates, Inc. Senior Biostatistician

3.0	
Updated to point to CIP V4.0 and ISO 14155 2020
 
 Changed "Safety Failure" to "Treatment Failure" Deleted previous statements in the "Center Pooling", no statistical analysis would be performed due to small sample sizes and single arm, but a subgroup analysis by regions will be presented. Added time courses to "Investigation Plan" section Modified "Determination of Sample Size" according to CIP 4.0 Update made in Subgroup Analysis Safety Evaluation – added 4 types of endpoints and device deficiencies; deleted this statement: "A literature review will be conducted to provide additional supporting evidence of the safety of the device." Added the definition of the event of clinically significant overcorrection. Added when to utilize CEC adjudication Added a new section: algorithm of neurological success in the last section "Statistical Appendices" 	
██████████, Medtronic Senior Principal Statistician

Version	Summary of Changes	Author(s)/Title
4.0	
 Added observational radiographic endpoints; Changed the ITT (intent-to-treat) population to the primary analysis population; Added additional analyses by comparing the postoperative measurements with the measurements prior to discharge Added an additional subgroup analysis by stratifying the primary endpoint outcome by degree of baseline curve flexibility Added PedsQL and SRS -22r scoring method 	
██████████ Medtronic Senior Principal Statistician

5.0	
 Clarified cobb angle to be main thoracic Added secondary endpoint to assess TL/L cobb angle Added observational radiographic endpoint to assess PT cobb angle Added Main Thoracic to cobb angle for clarity considering we are now also assessing PT and TL/L cobb angles. Added "If there is any additional interim analysis needed, the statistical analysis plan will be updated to document the need." Added abbreviations for PedsQL and SRS-22 Added investigator's assessment will be reported for device or procedure-related adverse events 	
██████████ Medtronic Senior Principal Statistician

6.0	
The content is adapted according to CIP 7.0 to reflect the changes due to the decision to discontinue the BRAIVE program. More specifically:
 
 Updated primary objective from demonstrating efficacy to a primary safety objective to summarize device-related adverse events up to 24-month visit Main Cobb angle is now a secondary endpoint Added Instrumented Cobb Angle as an endpoint 	
██████████ Senior Statistics Manager

Version	Summary of Changes	Author(s)/Title
	
 Added Secondary spine surgery up to 24-month visit and Device deficiency up to 24-month visit as secondary safety endpoints. Removal of the following endpoints: Individual Subject Success, PedsQL, shoulder imbalance endpoint, T1-L1 length, disc wedging angle and Neurological status. Sample size changed from 25 to 10. Removal of the subgroup analyses. 	

2. List of Abbreviations and Definitions of Terms

Abbreviation	Definition
AE	Adverse Event
CIP	Clinical Investigation Plan
SAP	Statistical Analysis Plan
HDE	Humanitarian Device Exemption
GMS	Growth Modulation System
SAE	Serious Adverse Event
PedsQL	Pediatric Quality of Life Inventory™
SRS-22	Scoliosis Research Society 22 Patient Questionnaire

3. Introduction

The Braive™ Growth Modulation System functions by using growth modulation to treat patients with immature spinal anatomy. The system is comprised of a flexible braid, which is affixed to the anterior spinal column using metallic vertebral body screws, plates, and set screws. As the patient grows, the braid maintains compressive forces on the vertebral bodies along the convex side of the curve to correct the curvature of the thoracic spine. The continued growth of the concave side brings the vertebral bodies back into alignment. As with devices that function using growth modulation, no fusion of the spine occurs. The Braive™ Growth Modulation System is designed to correct and preserve correction in a non-fusion manner to preserve the patient's growth potential.

This statistical analysis plan details the planned objectives and analyses to be performed to evaluate the safety and performance of the Braive™ Growth Modulation System when used in the treatment of juvenile and adolescent idiopathic scoliosis. The data obtained from this study may be used for regulatory purposes worldwide, in addition to possible publications.

4. Study Objectives

The purpose of this study was to establish probable benefit and evaluate the safety and preliminary effectiveness of the Braive™ GMS when used in the treatment of JIS and AIS.

In March 2023, Medtronic made the decision to discontinue the BRAIVE program. All sites, therefore, have been notified to discontinue study enrollment and there are no plans at this time to utilize collected data to obtain Humanitarian Device Exemption (HDE) approval.

This decision is not associated with any safety or efficacy observations from the study, and the study has not received stopping recommendations from the Data Monitoring Committee.

5. Investigation Plan

This is a prospective, multi-center, single-arm study of the Medtronic Braive™ GMS. As all subjects will have failed conservative care as per investigator's assessment, they will serve as their own controls. The baseline measurements will be collected prior to implantation of the device and compared against the measurements collected postoperatively. Data will be evaluated mainly for safety. Each subject will be followed until skeletally mature.

Clinical assessments will be completed at baseline (preoperatively), during surgery, and postoperatively at discharge, 3 months, 6 months, 12 months, 18 months, and 24 months, and then annually until subjects reach skeletal maturity (defined as Risser 5 as assessed by the investigator).

6. Determination of Sample Size

This study was designed to show that the investigational device can be used to obtain a statistically significant improvement (>0) in the Cobb angle. The initial sample size required to demonstrate a statistically significant improvement of Cobb angle at 24 months as compared to that in the preoperative visit is 24. Medtronic planned to treat 25 subjects (refer to SAP V5.0 for detail). Due to the decision to stop the enrollment early, the sample size is 10 at the time of this decision.

7. Statistical Methods

7.1 Study Subjects

7.1.1 Disposition of Subjects

Accountability tables will be generated to show, at each study visit, the number of subjects who might be expected to attend a given visit and the number and proportion who did attend. Visits occurring outside the windows will be considered protocol deviations. However, they will be included in the analysis.

7.1.2 Clinical Investigation Plan (CIP) Deviations

Any deviations from the clinical investigation plan will be summarized and discussed in the clinical study reports.

7.1.3 Analysis Sets

7.1.3.1 Primary Analysis Population

The primary analysis population will include all subjects who are enrolled and undergo the Braive™ GMS surgical procedure. The primary dataset will be used for all the analyses. For subjects who are treatment failures, the last postoperative observation before the first treatment failure will be carried forward for analysis of additional secondary endpoints (see section 7.9.1).

7.2 General Methodology

All data will be analyzed using descriptive statistics including but not limited to mean, standard deviation, frequency, percentage, and 95% confidence intervals, as appropriate for the scale and distribution of the endpoint.

7.3 Center Pooling

Since the sample size is relatively small and the study is a single-arm, it's not applicable to test the site effect. Data from all centers will be pooled together for the analyses.

7.4 Handling of Missing, Unused, and Spurious Data and Dropouts

All analyses will be conducted based on the observed data with no missing data imputation.

7.5 Adjustments for Multiple Comparisons

Since the nature of the analysis is descriptive, no adjustments for multiple comparisons will be made.

7.6 Demographic and Other Baseline Characteristics

Baseline data will include but are not limited to height, weight, age, and preoperative radiographic measurements. Demographics and other pre-treatment characteristics will be summarized and characterized with appropriate descriptive statistics. Categorical variables will be summarized using frequency and percentage. Continuous variables will be summarized using mean, median, standard deviation, minimum, and maximum.

7.7 Treatment Characteristics

Operative data will include but are not limited to patient position, surgical approach, whether an access or general surgeon was used for the approach, number of incisions, total fluoroscopic time, implant details, and imaging system used for intra-op. Operative data will be summarized and characterized with appropriate descriptive statistics. Categorical variables will be summarized using frequency and percentage. Continuous variables will be summarized using mean, median, standard deviation, minimum, and maximum.

7.8 Interim Analyses

Due to the decision to stop the study enrollment, a final analysis will be conducted when all subjects have reached skeletal maturity. An interim analysis may be conducted when everyone reaches 24-month visit in addition to the progress reports required by the FDA.

7.9 Evaluation of Objectives

The primary objective of this study has been changed from demonstrating efficacy to a primary safety objective to summarize device-related adverse events up to 24-month visit. Please refer to section 7.10 Safety Evaluation for detail.

7.9.1 Analysis for Additional Secondary Endpoints

Additional secondary endpoints in addition to the secondary safety endpoints outlined in the section 7.10.2 are listed below:

- Change from baseline in main thoracic Cobb angle at all available postoperative time points
- Change from baseline in proximal thoracic Cobb angle at all available postoperative timepoints
- Change from baseline in thoracolumbar/lumbar Cobb angle at all available postoperative timepoints
- Change from post-op baseline in Instrumented Cobb Angle at all available postoperative time points
- Change from baseline in thoracic kyphosis at all available postoperative timepoints
- Change from baseline in Lumbar Lordosis at all available postoperative timepoints
- Change from baseline in coronal balance at all available postoperative timepoints
- Change from baseline in Sagittal Balance at all available postoperative timepoints
- Change from baseline in total vertical thoracic spine height (T1- T12) at all available postoperative timepoints
- Change from baseline in total vertical spine height (T1-S1) at all available postoperative timepoints
- Change from baseline in Scoliosis Research Society-22 Patient Questionnaire (SRS-22) at all available postoperative timepoints
- Status of return to full activity within 3 months per SRS-22

For the additional secondary endpoints related to the change from the baseline, when the distribution of data is approximately normally distributed, the change from baseline will be tested using a paired-

sample t-test. When the distribution of the data is non-normal, a Wilcoxon signed-rank test may be used in place of the paired t-test. In addition, the descriptive statistics including but not limited to mean, standard deviation, median, minimum and maximum will be calculated and presented. For “Status of return to full activity within 3 months per SRS-22”, the number and percentage of subjects returned to full activity within 3 months will be calculated and presented.

Additional analysis will be performed by comparing the postoperative measurements at follow-up visits with the measurements at immediate post-op.

7.9.2 Subgroup Analyses

No subgroup analysis will be conducted.

7.10 Safety Evaluation

All adverse events will be reviewed by Medtronic safety representative for safety assessments.

7.10.1 Primary Safety Endpoint

The primary safety endpoint is device-related adverse events up to 24-month visit postoperatively. Sponsor’s classification and investigator’s assessment will be used for this endpoint. The event rate along with the 2-sided 95% confidence interval will be calculated and presented.

In addition, all device-related adverse events up to skeletal maturity (Riser score 5) will be summarized.

7.10.2 Secondary Safety Endpoint

The secondary safety endpoints include

- Procedure-related adverse events up to 24-month visit. Sponsor’s classification and investigator’s assessment will be used for this endpoint.
- Secondary spinal surgeries related to the device up to 24-month visit. Sponsor’s classification and investigator’s assessment will be used for this endpoint.
- Device deficiency up to 24-month visit.

For these secondary safety endpoints, the event rate along with the 2-sided 95% confidence interval will be calculated and presented.

In addition, all procedure-related adverse events up to skeletal maturity, all secondary spinal surgeries related to the device up to skeletal maturity and device deficiency up to skeletal maturity will be summarized.

7.10.3 Adverse Events and Device Deficiencies

A listing of all AEs, SAEs, device or procedure related AEs and SAEs and device deficiencies, secondary spinal surgeries and death will be generated. In addition, summaries of AEs, both overall and by visit, will be provided.

Summaries will be presented for all AEs, SAEs, device or procedure-related AEs, device or procedure-related SAEs and device deficiencies. Time course distributions will be provided in addition to cumulative summaries. Time course distributions will be based on the surgery date of the subject and onset dates of AEs, resulting in continuous time intervals. For overall summaries, a subject reporting the outcome at least once during the study period will be included in the frequency count. The percentage of subjects reporting the event at least once at up to 12-month visit, 24-month visit and skeletal maturity will be reported, and the denominator used in this calculation will be the total number of subjects who are enrolled and who receive the study treatment.

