9.2.5. Risser Score

Risser Score will be assessed by the investigator to evaluate the skeletal maturity of the subject in accordance with the following definitions:

Grade 0: No iliac apophysis visible.

Grade 1: Initial appearance of ossification of the iliac apophysis.

Grade 2: Migration halfway across the top of the iliac wing.

Grade 3: Three-fourths of the distance.

Grade 4: Ossification crossing the iliac wing, but not fused to the ilium.

Grade 5: Complete ossification of the iliac apophysis with fusion to the ilium.

When grade 5 is reached on or after 24-month follow up visit, subject will be exited from the study.

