13.6. Safety Analysis

13.6.1. Primary Safety Endpoint

The primary safety endpoint is device-related adverse events up to 24-month visit postoperatively.

The number of events, the number and percentage of subjects experiencing device related AE up to 24 months postoperatively will be presented.

In addition, all device-related adverse events up to skeletal maturity (Risser 5) will be summarized.

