13.6.3. Adverse events

A listing of all AEs will be provided, and a narrative of each device or procedure related AEs, secondary spinal surgeries, and death will be generated. In addition, summaries of AEs, both overall and by visit, will be provided.

Summaries will be presented for all AEs, SAEs, device or procedure-related AEs and device or procedure-related SAEs. Time course distributions will be provided in addition to cumulative summaries. Time course distributions will be based on the surgery date of the subject and onset dates of AEs, based on continuous time intervals. For overall AE summaries, a subject reporting the outcome at least once during the study period will be included in the frequency count. The percentage of subjects reporting the event at least once during the study period will be reported, and the denominator used in this calculation will be the total number of subjects who are enrolled and who receive the study treatment.

For AE summaries by visit, a subject reporting the outcome at least once during each visit window will be included in the frequency count. The percentage of subjects reporting the outcome at least once during each visit window will be reported, and the denominator used in this calculation will be the number of subjects who have any data reported at that visit (clinical or safety).

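### The 24-month safety rates divide by all 10 treated subjects with no count of how many were followed that long, and a subject with no 24-month visit has no cut-off date

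*SAP*

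**What the plan says.** **Denominator.** SAP 7.10.3 reports the percentage of subjects with at least one event up to the 12-month visit, the 24-month visit and skeletal maturity, and "the denominator used in this calculation will be the total number of subjects who are enrolled and who receive the study treatment". It covers device- or procedure-related adverse events and device deficiencies. SAP 7.10.4 handles secondary spinal surgeries in a similar way, and protocol 13.6.3 uses the same denominator for overall summaries.

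**Rates with intervals.** SAP 7.10.1 promises an event rate with a 95% interval for the primary endpoint. SAP 7.10.2 does the same: "For these secondary safety endpoints, the event rate along with the 2-sided 95% confidence interval will be calculated and presented". Neither section names a denominator or an interval method. SAP 7.1.3.1 and protocol 13.3 define one population, all enrolled subjects who had the procedure, and use it for every analysis.

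**Incomplete follow-up.** SAP 7.4 says "All analyses will be conducted based on the observed data with no missing data imputation", and protocol 13.5 agrees. Neither document says how to treat a subject without 24 months of safety follow-up in these rates. Protocol 9.9.1 provides for remote adverse event follow-up after withdrawal only if the subject agrees.

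**Cut-off.** SAP 7.10.1: "The primary safety endpoint is device-related adverse events up to 24-month visit postoperatively". Protocol 13.6.1 opens with the same sentence, but then says that "the number and percentage of subjects experiencing device related AE up to 24 months postoperatively will be presented". Protocol Table 6 allows 90 days either side of the 24-month visit. On late or early visits, SAP 7.1.1 says: "Visits occurring outside the windows will be considered protocol deviations. However, they will be included in the analysis".

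**The concern.** The device-related event rate is now the primary result of a study with 10 treated subjects. An event-free early leaver stays in its denominator and adds nothing to its numerator, so the device can look safer than the follow-up supports. This is hardest to see with zero events: the table reads 0 of 10 whether ten subjects or seven were observed.

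The tables that show follow-up do not sit with this rate. The attendance table in SAP 7.1.1 counts visits. The by-visit percentages in protocol 13.6.3 use subjects with data at that visit, but they describe each visit window, not the cumulative 24-month result.

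The cut-off matters less, but it needs settling before the tables are programmed. Two programmers could class the same late event differently, and a visit-based cut-off gives no date for a subject who never has the visit.

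**Working it through.** **Inputs.** Ten treated subjects (SAP section 6). Visit window of 90 days either side (protocol Table 6). The documents give no safety rate, interval or dropout count, so there is no stated figure to reproduce. Assumed for illustration: k = 0 to 3 event-free leavers, and a 24-month risk of 11.2% or 30%. The 11.2% is the 13/116 overcorrection figure in protocol 4.1. It comes from other tethering devices, partly with one year of follow-up, and serves only as a low value.

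**Step 1: all treated against those followed.** Exact (Clopper-Pearson) 95% limits. For zero events the upper limit is 1 − 0.025^(1/n): with n = 10 this is 30.8%, with n = 8 it is 36.9%. The n = 10 row is what the plan would report in every case.

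| Leavers k | n = 10 − k | 0 events, upper limit | 1 event | 2 events |
|---|---|---|---|---|
| 0 | 10 | 30.8% | 10.0% (0.3 to 44.5) | 20.0% (2.5 to 55.6) |
| 1 | 9 | 33.6% | 11.1% (0.3 to 48.2) | 22.2% (2.8 to 60.0) |
| 2 | 8 | 36.9% | 12.5% (0.3 to 52.7) | 25.0% (3.2 to 65.1) |
| 3 | 7 | 41.0% | 14.3% (0.4 to 57.9) | 28.6% (3.7 to 71.0) |

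**Step 2: does the time of leaving matter?** Take two events.
- If the leavers go before the first event, Kaplan-Meier equals 2/(10 − k): 22.2%, 25.0% and 28.6% for k = 1, 2, 3.
- If they go between the two events, Kaplan-Meier is 1 − (9/10) × [1 − 1/(9 − k)]: 21.3%, 22.9% and 25.0%.

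In these cases the crude 20.0% and the followed-subject rate bracket Kaplan-Meier. All the point estimates lie inside the crude interval of 2.5% to 55.6%.

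**Step 3: expected size of the bias.** Constant hazard, F(t) = 1 − (1 − p)^(t/730), leavers at day 182. Expected crude rate = [(10 − k) × F(730) + k × F(182)]/10.
- p = 11.2%: F(182) = 2.9%. For k = 1, 2, 3 the result is 10.4%, 9.5%, 8.7%.
- p = 30%: F(182) = 8.5%. The result is 27.9%, 25.7%, 23.6%.

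One leaver therefore costs about 0.8 or 2.1 points.

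**Step 4: the cut-off.** 730 ± 90 puts an in-window visit at about day 640 to 820. With visits spread evenly over that range, the average rate under the visit rule is the same as under a day-730 rule (11.2% and 30.0%). The mean chance that one subject is classed differently is 0.0065 or 0.0154. For any of 10 subjects it is 1 − (1 − 0.0065)^10 = 6%, or 1 − (1 − 0.0154)^10 = 14%.

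A day-820 cut-off for everyone would raise the expected rate from 11.2% to 12.5%, or from 30.0% to 33.0%. That is 1.3 or 3.0 points, more than the one-leaver bias in step 3.

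**The case against.** The strongest reply is that nothing is broken. An all-treated denominator is usual for adverse event tables, and the SAP calls its analysis descriptive. With 10 subjects the reader also gets attendance tables, a listing of all adverse events and time courses. Remote contact is available under protocol 9.7, and no dropout is on record. Most of this stands, and it limits the size of the point. What it does not supply is a count of subjects followed, placed beside the cumulative rate.

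Three stronger readings are tempting, and the documents do not support them:

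- A reader might infer that the denominator contradicts the no-imputation rule in SAP 7.4. Observed events over subjects treated uses observed data only. What is missing is a rule for incomplete follow-up.
- A reader might infer that the SAP and the protocol conflict on the cut-off. The first sentence of protocol 13.6.1 matches SAP 7.10.1, so the variation lies mainly within the protocol. Its references to 24 months can be read as shorthand for the scheduled visit.
- A reader might infer that exit at skeletal maturity cuts follow-up short. Protocol 9.2.5 says: "When grade 5 is reached on or after 24-month follow up visit, subject will be exited from the study". Under the visit-based cut-off such a subject is complete. A gap appears only if a fixed day is imposed.

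**Conclusion.** The point holds as a cheap improvement. It is not an error that invalidates the analysis. The denominator is settled by SAP 7.10.3 together with SAP 7.1.3.1. Its consequence for event-free early leavers follows from having no rule for incomplete follow-up, and the direction of the bias is certain.

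The size is not known. It is zero with complete follow-up. With one to three assumed leavers, the zero-event upper limit rises from 30.8% to between 33.6% and 41.0%, and a two-event rate of 20.0% becomes at most 28.6%. Both shifts are modest beside the interval at n = 10. The expected-rate figures also assume a constant hazard and exit at six months.

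The cut-off wording is the smaller matter. The average rate does not change, and the chance that any subject is reclassified is about 6% to 14%. The real gap there is the subject with no 24-month visit.

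**What to change.** In SAP 7.10.1 to 7.10.3, with matching words in protocol 13.6.1 and 13.6.3:

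1. Name the denominator in 7.10.1 and 7.10.2. Keep the crude n/10, with an exact 95% interval.
2. Beside each 24-month rate, give the number of subjects who either had the event or were followed for adverse events through the 24-month visit (the visit itself, remote contact at that time, or any later adverse event contact). Give the rate with an exact interval on that number. A footnote could say how many had the 24-month X-ray, since the remote contact in protocol 9.7 does not include one.
3. Optionally, add a Kaplan-Meier 24-month estimate censored at last adverse event contact.
4. Reconcile the protocol to the SAP's visit-based cut-off, the date of the 24-month visit. Findings on that visit's X-ray then count, and a Risser 5 exit there is complete follow-up. For the analysis of a subject who misses the visit, use the end of its window (day 820), or last adverse event contact if earlier.

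Do not apply day 820 to everyone. A subject who exits at a day-640 visit would be unobserved for 180 days yet counted as event-free.

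**Cost.** Some wording and one extra table line, with a wider interval and possibly a slightly higher stated rate. Event dates are collected and time courses already run from the surgery date. Protocol 9.9.2 asks for a last-contact date for living subjects lost to follow-up. For withdrawals none is specified, so the study exit date would serve, assuming the exit form records it.
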